8.4.3.2 Evaluations at Withdrawal

For any subject who is withdrawn before completing all treatment visits, the Investigator should:

- perform all the procedures scheduled for the EOS visit (ie, week 28 visit [[Section 9.6](#)]). The week 28/EOS assessments will be performed 8 weeks (± 7 days) after the last dose of IP (unless the subject withdraws consent to do so). Computed tomography is only required at early withdrawal if it has not been performed within the previous 28 days. **Computed tomography is to be performed before the start of new anti-cancer treatment.**
- complete all appropriate electronic case report form (eCRF) screens, providing the date of and explanation for the subject's withdrawal/discontinuation.
- when indicated, arrange for appropriate follow up and/or alternative medical care of the discontinued subject.

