9.6 Week 28/End of Study

For subjects completing the treatment phase, the EOS visit will be at week 28, 8 weeks (± 7 days) after the last dose of IP. For subjects who do not complete the treatment phase, the EOS visit will be 8 weeks (± 7 days) after the last dose of IP. **Subjects who discontinue from the study due to disease progression should have a CT scan (as described below) prior to initiation of new anti-cancer treatment, if deemed clinically acceptable.**

At the EOS visit (**week 28 or 8 weeks after the last dose of IP**), the following assessments will be performed:

- physical examination, including evaluation of body systems
- vital signs (systolic and diastolic blood pressure, pulse, respiration rate, and temperature)
- standard 12-lead ECG
- ECOG performance status
- clinical disease assessment
- CT (not required if performed within the previous 4 weeks) of the neck (if palpable lymph node >1.0 cm or if performed at baseline), chest, abdomen, and pelvis.
- bone marrow biopsy (only required if bone marrow involvement is identified at baseline **for CR confirmation; if a confirmatory bone marrow assessment is not obtained, these subjects should be considered as only having a PR**). **The bone marrow biopsy can be performed at ± 14 days in relation to the study visit date.**
- clinical laboratory testing, including serum chemistry and hematology
- collection of samples for PK, antidrug antibodies, CD19+ cell count, and IgG and IgM levels

Any changes in concomitant medications since the last assessment will be recorded.

Any additional treatment for lymphoma will be recorded. All AEs, including increases in severity or frequency of pre-existing conditions, will be recorded in the eCRF through the week 28 visit. SAEs will be reported as outlined in [Section 11.2.2](#). Any SAEs ongoing at week 28 will be followed until they resolve or are considered chronic or stable.

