12.6.7.4 Progression-free Survival and Overall Survival

Progression-free survival is defined as the time from randomization until the first occurrence of disease progression or death from any cause according to the standard criteria in [Cheson et al, 1999](#). For subjects alive and progression-free at the week 28/EOS visit, PFS will be censored at the date of the last tumor evaluation demonstrating lack of progression.

Overall survival is defined as the time from randomization to death from any cause. Subjects who have not died before the week 28/EOS visit will be censored for OS at the last known date alive on or prior to EOS.

For these time-to-event outcomes, the hazard ratio and 1-sided 95% and 97.5% CIs for ABP 798 relative to rituximab will be estimated from a Cox model stratified by stratification factors. In addition, Kaplan-Meier curves and median survival time will be provided descriptively.

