5. DEFINITIONS

5.1 GENERAL

Actual Treatment Received

Defined according to the majority of doses received.

Change From Baseline

Change from baseline is defined as (value at post-baseline visit – value at baseline).

Disease Duration

The disease duration is the number of months from the date of original diagnosis of NHL to the date of randomization, which will be derived based on the table below. No imputation will be done for disease diagnosis date, but to avoid a disease duration of zero, 1 month may be added.

Table 1. Calculation for Disease Duration

Observed Portion	Missing Portion	Formula to Calculate Duration
Year, Month, Day		(Date of Randomization – Date of Diagnosis + 1)*12/365.25
Year, Month	Day	[Year (Date of Randomization) – Year (Date of Diagnosis)]*12 + [Month (Date of Randomization) – Month (Date of Diagnosis)]*
Year	Month, Day	[Year (Date of Randomization) – Year (Date of Diagnosis)]*12*

*If the duration equals 0, add 1 month.

Dose Delay

A dose will be considered delayed when the IP administration eCRF indicates that a dose was given but a reason for dose delay is present.

Dose Withheld

A dose will be considered withheld when the IP administration eCRF indicates that no dose is given and a reason for dose delay is present.

Duration of IP exposure

Duration of IP exposure in weeks will be defined as (end of study date – date of first dose of IP + 1) / 7.

Follicular Lymphoma International Prognostic Index and Risk Categories

The follicular lymphoma international prognostic index (FLIPI) is based on the following 5 prognostic factors:

- Age (≥ 60 years)
- Ann Arbor Disease Stage (Stage III-IV, Stage III includes IIIE, IIIES, and IIIS)
- Hemoglobin level (<120 g/L)
- Serum lactate dehydrogenase level ($>$ upper limit of normal)
- Number of nodal sites (> 4)

Subjects with 0-1 risk factors are defined as low risk, subjects with 2 risk factors are defined as intermediate risk, and subjects with 3 or more risk factors are defined as high risk.

Study Baseline

For safety endpoints, the study baseline is defined as the last non-missing assessment taken prior to the first dose of IP. In cases where baseline assessments are taken on the same day as IP and

no times are reported, it will be assumed that these assessments are taken prior to IP being administered. For subjects who are randomized but not dosed after the randomization, the baseline is defined as the last non-missing assessment prior to or on the date of randomization.

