5.4 SAFETY

Event of Interest (EOI)

An EOI is defined as a noteworthy event for a particular product or class of products that a sponsor may wish to monitor carefully. It could be serious or non-serious, and could include events that might be potential precursors or prodromes for more serious medical conditions in susceptible individuals (Council for International Organizations of Medical Sciences (CIOMS) VI, 2005). The EOIs that will be monitored in this study are:

- infusion reactions
- tumor lysis syndrome
- cardiac disorders
- serious infections
- severe mucocutaneous reactions
- hematological toxicity
- progressive multifocal leukoencephalopathy
- GI perforation

AE preferred terms that are potentially representative of the EOI will be retrieved for review and analysis using the latest version of pre-specified Standardized MedDRA Queries (SMQs) if available.

Infusion reaction and tumor lysis syndrome EOIs will be summarized separately for:

- all events and
- events with onset day coincident with first IP infusion or the day after the first IP infusion.

If no SMQ is available for use as a search tool for a given EOI (e.g, infusion reactions) a customized search strategy will be developed and the preferred terms used in that search will be provided in an appendix to the SAP prior to the database lock.

Exposure-adjusted Incidence Rates of Adverse Events

Exposure-adjusted incidence rate is calculated as the number of subjects in a treatment group that experienced the event at least once divided by the total subject exposure times in the group. For subjects who experience the event, the exposure time is calculated as the time from the first dose date of IP to the onset of the first event. For subjects who do not experience the event, the exposure time is calculated as the time from the first dose of IP to the minimum of the end of study (EOS) visit date and death date.

Last Known Date Alive

The last known date alive will be the maximum of: end of study date, non-fatal AE start and stop dates, IP administration dates, serum chemistry and hematology sample collection dates, ADA sample collection dates, concomitant medication dates, vital sign dates, PK sample collection dates, and NHL lesion assessment dates.

Overall Survival (OS)

On-study OS is defined as the time from randomization to the date of death. Subjects who have not died before the week 28/EOS visit will be censored for OS at the last known date alive on or prior to EOS.

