5.5 IMPUTATION FOR PARTIAL OR MISSING DATES

Partial or missing admission and discharge dates for hospitalizations will not be imputed.

If dates are missing or incomplete for an AE (including deaths) or concomitant medication, the following algorithm will be used for imputation:

Table 2. Imputation Rules for Partial or Missing Start Dates

	Stop Date			
Start Date	Complete: yyyymmdd	Partial: yyyymm	Partial: yyyy	missing

		<1 st dose	≥1 st dose	<1 st dose yyyyymm	≥1 st dose yyyyymm	<1 st dose yyyy	≥1 st dose yyyy	
Partial: yyyyymm	= 1 st dose yyyyymm	2	1	n/a	1	n/a	1	1
	≠ 1 st dose yyyyymm		2	2	2	2	2	2
Partial: yyyy	= 1 st dose yyyy	3	1	3	1	n/a	1	1
	≠ 1 st dose yyyy		3		3	3	3	3
Missing		4	1	4	1	4	1	1

- 1 = Impute the date of first dose
- 2 = Impute the first of the month
- 3 = Impute January 1 of the year
- 4 = Impute January 1 of the stop year

Note: If the start date imputation leads to a start date that is after the stop date, then do not impute the start date.

Imputation rules for partial or missing stop dates:

1. Initial imputation
 - a. For partial stop date “mmyyyy”, impute the last of the month.
 - b. For partial stop date “yyyy”, impute December 31 of the year.
 - c. For completely missing stop date, do not impute.
2. If the stop date imputation leads to a stop date that is after the death date, then impute the stop date as the death date.
3. If the stop date imputation leads to a stop date that is before the start date, then there is a data error and do not impute the stop date (i.e. set the stop date as missing).

Imputation rules for partial or missing death dates:

1. If death year and month are available but day is missing:

- a. If “mmyyyy” for last contact date = “mmyyyy” for death date, set death date to the day after the last contact date.
 - b. If “mmyyyy” for last contact date < “mmyyyy” for death date, set death date to the first day of the death month.
 - c. If “mmyyyy” for last contact date > “mmyyyy” for death date, data error and do not impute.
2. If both month and day are missing for death date or a death date is totally missing, set death date to the day after the last contact date.

The imputed dates will be used to assess whether AEs should be considered as treatment-emergent and if concomitant medications should be included in the safety summaries, however the original, partial dates will be included in data listings.

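### The OS censoring rule counts the end of study date as evidence of life, so for a subject lost without an EOS visit it can credit survival time that no contact supports

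*SAP*

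**What the plan says.** SAP 5.4 defines the date: "The last known date alive will be the maximum of: end of study date, non-fatal AE start and stop dates, IP administration dates". The list goes on to serum chemistry and hematology samples, ADA samples, concomitant medication, vital signs, PK samples and lesion assessments. Under Overall Survival in the same section, those not known to be dead by week 28 or end of study "will be censored for OS at the last known date alive on or prior to EOS". Protocol 12.6.7.4 has the same censoring sentence and does not define the term.

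Three closely related dates appear, none of them defined:

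- *End of study date*, in the list above and in SAP 5.1: "Duration of IP exposure in weeks will be defined as (end of study date" and so on.
- *EOS visit date*, in the exposure-adjusted rates of SAP 5.4, where follow-up of subjects without the event ends at "the minimum of the end of study (EOS) visit date and death date".
- *Last contact date*, in SAP 5.5 for incomplete death dates, where one instruction is to "set death date to the day after the last contact date". It is not in the list for last known date alive.

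For a subject withdrawn early, Protocol 8.4.3.2 asks the site to complete the eCRF, "providing the date of and explanation for the subject's withdrawal/discontinuation". On the timing of the visit, Protocol 9.6 says: "For subjects who do not complete the treatment phase, the EOS visit will be 8 weeks (± 7 days) after the last dose of IP".

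**The concern.** A last known date alive should be the latest date on which there was evidence that the subject was alive. Doses, samples, vital signs and scans are such evidence. An end of study date is evidence only if someone saw or spoke to the subject on that date. If it is the day a site closes the record of a subject it cannot reach, it is an administrative date.

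With that date inside the maximum, the contact dates no longer protect against it. A subject of unknown vital status could stay in the OS risk set as alive past the last contact. If some deaths in that interval never became known, survival would be overstated, and the arms would be affected unequally if loss differed between them. OS is a stated safety endpoint, reported with a hazard ratio, 1-sided 95% and 97.5% confidence limits and Kaplan-Meier curves.

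The SAP handles similar cases differently. PFS is censored at the last disease evaluation showing no progression, and incomplete death dates are imputed by reference to last contact.

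**Working it through.** The documents give no OS event count, loss rate or power figure, so there is no stated figure to reproduce. The check covers the date rule first and then its possible size.

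**1. End of study date and EOS are the same date, E.** Let d1, d2, … be the other listed dates. The cap can be read in two ways:

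- min(max(E, d1, d2, …), E) = E, because the inner maximum is at least E.
- The largest of {E, d1, d2, …} not after E is E, because E is in the set.

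A check on 100,000 random date sets found no exception under either reading. The contact dates are then redundant for OS censoring. The cap still does something: it removes dates after EOS, such as a late AE stop date.

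**2. The two dates differ.** For a subject with an EOS visit on day 190 and an end of study date of day 204, the result is day 190, which is a real contact. If the end of study date is missing, the contact dates decide. So the identity in step 1 is conditional.

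**3. A subject lost without an EOS visit.** Assume dose 4 on day 22 and no contact afterwards. If EOS means the visit, there is no cap, and the maximum cannot fall below the recorded end of study date.

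| Recorded end of study date (assumed) | OS censored at | Unobserved time |
|---|---|---|
| Day 22 (last contact) | Day 22 | 0 days |
| Day 78 (8 weeks after last dose) | Day 78 | 78 − 22 = 56 days |
| Day 99 (closed after the week 12 visit is missed) | Day 99 | 99 − 22 = 77 days (11 weeks) |
| Day 190 (near week 28) | Day 190 | 190 − 22 = 168 days (24 weeks) |

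If the cap is instead read as the scheduled EOS visit of Protocol 9.6, it falls at day 22 + 56 = 78 ± 7, so no later than day 85. The credit is then at most 85 − 22 = 63 days.

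SAP 5.5 gives a contrast. If the same subject were known to have died but the death date was wholly missing, the death would be placed on day 23. With vital status unknown and closure on day 99, the subject is censored as alive on day 99.

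**4. Trial level.** Inputs: 250 subjects and a nominal 28 weeks (documents); loss fraction f and mean gap g in weeks (assumed). Excess subject-weeks = 250 × f × g. Nominal follow-up = 250 × 28 = 7,000 subject-weeks.

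| f | g | Excess | Share of 7,000 |
|---|---|---|---|
| any | 0 | 0 | 0% |
| 2% | 4 | 20 | 0.3% |
| 5% | 8 | 100 | 1.4% |
| 10% | 11 | 275 | 3.9% |

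An extreme case of 10% loss, all with a 24-week gap, gives 600 subject-weeks, or 600/7,000 = 8.6%. It requires every lost subject to disappear after dose 4 and be closed only near week 28.

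**5. Effect on the arm comparison.** Assume equal constant death rates and no recorded deaths in the gap. The apparent rate ratio is (1 − f₁g/28)/(1 − f₂g/28).

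- Equal loss: 1.
- 10% vs 5% loss, 8 weeks: 0.9714/0.9857 = 0.986.
- 10% vs 5% loss, 11 weeks: 0.9607/0.9804 = 0.980.
- 10% vs 5% loss, 24 weeks: 0.9143/0.9571 = 0.955.

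**The case against.** A reader might infer that the rule always returns the end of study date. The documents do not support that. It needs the end of study date and EOS to be the same non-missing date, and the SAP never equates them. Step 2 shows a case where they differ and the result is correct. This limits the claim, but it does not help the lost subject, who has no EOS visit to supply a cap.

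A reader might also infer that lost subjects are in fact credited with survival nobody observed. The documents do not establish this either. It happens only if the recorded date is later than last contact. Protocol 8.4.3.2 asks for a withdrawal or discontinuation date, but does not call it the end of study date and does not mention administrative closure. SAP Section 1 says the plan is to be read with the eCRFs, which are not available here. If the form records last contact, the gap is zero. A consent withdrawal date may itself be a contact.

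The consequences are also limited. A death in the gap is missed only if it is never learned of, and Protocol 8.4.3.1 allows publicly available data after consent withdrawal where permitted. The synopsis calls the OS confidence limits descriptive, and Protocol 12.6.4 and SAP 9.5.3 confine inference to the primary endpoint. SAP1.1 is to be followed by SAP2, and the dataset specifications (SAP Section 10) might settle the derivation.

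All of this stands as a limit on size and certainty. The SAP still states a rule under which a date with no contact behind it can set OS censoring, and nothing in the documents prevents that.

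**Conclusion.** The point holds as a low-severity weakness in a stated rule. Where the end of study date and EOS coincide, the contact dates in SAP 5.4 cannot affect OS censoring. For a subject lost without an EOS visit, the recorded end of study date sets the result with or without evidence of life. Whether unobserved time is actually added depends on how the eCRF records that date.

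Under assumed loss of 2% to 10% and an assumed gap of 0 to 11 weeks, the excess is 0% to about 4% of OS follow-up. The hazard ratio is unaffected by equal loss and changes by about 2% with 10% vs 5% loss and an 11-week gap. The primary ORR analysis is not touched. An established survival bias cannot be claimed from these documents.

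**What to change.** In SAP2:

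- Take *end of study date* out of the maximum. Count the EOS date only if the EOS visit took place.
- Otherwise censor OS at the latest documented contact on or before EOS: dose, sample, vital sign, lesion assessment, complete AE or concomitant medication date, documented telephone contact, or dated consent withdrawal.
- Use this same date as the *last contact date* in Section 5.5, and say what EOS means as a cap when no visit took place.
- Keep the eCRF end of study date for disposition.

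Telephone contact needs to be named, because a subject confirmed alive by phone but not seen would otherwise be censored too early. Protocol 14.2 already requires contacts that yield significant clinical information to be documented. Whether the eCRF has a field for them should be checked.

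The cost is a short SAP2 text change and one derivation. The other dates come from data the study already collects. OS follow-up for lost subjects may become slightly shorter. The rule gives the intended result whichever way the eCRF defines the end of study date.

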10 METHODS OF ASSESSMENT

10.1 Response Assessments

Response to treatment will be assessed according to standardized criteria ([Cheson et al, 1999](#)). At the times indicated in [Table 1](#), Investigators will assess the status of each subject's follicular B-cell NHL. Assessment will include physical examination and radiographic examination. Computed tomography scan is the preferred method for radiographic tumor assessment. For subjects with contraindications to the contrast agent, the decision as to whether a non-contrast CT is used should be based on anatomic location of the disease and comparability with images previously taken in the course of the study.

For radiographic assessments, the same method of assessment and the same technique (eg, scan type, scanner, subject position, dose of contrast, injection/scan interval) should be used to characterize each identified and reported lesion at baseline. However, if a subject is imaged without contrast at baseline, subsequent assessments should be performed with contrast, unless the subject cannot tolerate the contrast.

Copies of all scheduled and unscheduled screening and on-study CT scans performed to monitor or diagnose NHL must be submitted to the central imaging vendor. This includes any such images deemed to be negative by the local radiologist and any standard-of-care or routine disease monitoring images performed, even if not specified by the protocol. Detailed procedures for image management will be provided in the study manual.

Clinical disease assessments, **which will be performed in conjunction with physical examinations**, will be performed by the investigator or sub-investigator and will be submitted to the central imaging vendor, if applicable.

Determination of response is outlined in [Section 17.2](#).

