1. INTRODUCTION

This statistical analysis plan (SAP) describes the statistical methods to be used during the reporting and analyses of data collected under Amgen Inc. Protocol 20130109, titled “A Randomized, Double-Blind Study Evaluating the Efficacy, Safety, and Immunogenicity of ABP 798 Compared with Rituximab in Subjects with CD20 Positive B-cell Non-Hodgkin Lymphoma (NHL).”

This SAP should be read in conjunction with the study protocol and electronic Case Report Forms (eCRFs). This version of the plan has been developed using the protocol dated 07 January 2016 version 3.0 and eCRFs dated 17 SEP 2014. Any further changes to the protocol or eCRFs may necessitate updates to the SAP.

The SAP is to be developed in two stages. The purpose is to “finalize” a SAP so that programming can start earlier in the process. Versions of the SAP up to initial sponsor approval will be known as SAP1. SAP1.1 is issued to reflect protocol version 3.0. Changes following approval of SAP1.1 will be tracked in the SAP Change Log and a final version of the SAP, known as SAP2, will be issued for Amgen’s approval prior to database lock.

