Progression-free Survival (PFS)

PFS is defined as the time from randomization until the first occurrence of disease progression per 1999 IWG-NHL criteria or death from any cause. For subjects alive and progression-free at the week 28/EOS visit, PFS will be censored at the date of the last disease evaluation demonstrating lack of progression. Subjects who have no post-baseline disease assessments will have their PFS times censored on the date of randomization. PFS will be calculated separately based on the central, independent, blinded radiologists' and oncologist's assessments and the investigator's assessment of progression.

Treatment-emergent Adverse Event

A treatment-emergent AE is defined as an AE that begins or increases in severity or frequency on or after the date of first IP and up to the EOS visit.

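### The SAP's PFS censoring rule for subjects with no post-baseline assessment is not limited to living subjects, so as written it censors deaths that the plan defines as events

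*SAP*

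**What the plan says.** SAP section 5.4 (Safety) treats PFS in three steps.

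- Event: "PFS is defined as the time from randomization until the first occurrence of disease progression per 1999 IWG-NHL criteria or death from any cause".
- General censoring: "For subjects alive and progression-free at the week 28/EOS visit, PFS will be censored" at the date of the last disease evaluation that showed no progression.
- No assessment after baseline: "Subjects who have no post-baseline disease assessments will have their PFS times censored on the date of randomization".

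The paragraph applies to both the central and the investigator versions of PFS.

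Protocol section 12.6.7.4 gives the same event definition, "the time from randomization until the first occurrence of disease progression or death from any cause", and the same general censoring rule: "For subjects alive and progression-free at the week 28/EOS visit, PFS will be censored at the date of the last tumor evaluation". It has no separate rule for subjects who were never assessed after baseline.

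For comparison, SAP section 5.4 says of survival: "On-study OS is defined as the time from randomization to the date of death". That definition does not depend on disease assessments.

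SAP section 9.8.6 gives the PFS methods: Kaplan-Meier estimates, and a stratified Cox model with 1-sided 95% and 97.5% limits. SAP section 5.5 imputes partial death dates. Neither says whether death or the no-assessment rule takes precedence.

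**The concern.** The second step is conditional on being alive and the third is not. A subject who is dosed and dies before any post-baseline disease assessment therefore meets the event definition in the first step and the censoring rule in the third. Two programmers could derive PFS differently from this paragraph. The literal derivation removes the earliest deaths from the PFS hazard ratio and the Kaplan-Meier curves, although both documents define those deaths as events.

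The size of the affected window depends on what counts as a disease assessment, which the sentence does not say. CT is scheduled at weeks 12 and 28, so if a scan-based assessment is meant, deaths up to about week 12 are exposed. Protocol Table 1 and section 9.3 also schedule clinical disease assessments at weeks 2, 3 and 4, and protocol section 10.1 says that these "will be performed by the investigator or sub-investigator and will be submitted to the central imaging vendor, if applicable". If they count, the window closes at about week 2.

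PFS is a listed safety endpoint, so the question is whether that safety summary counts every death it is defined to count.

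**Working it through.** **Reading the rules together.** Take a dosed subject who dies with no disease assessment after baseline.

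| Rule | Status of the subject |
|---|---|
| PFS event definition (SAP 5.4; protocol 12.6.7.4) | Event on the date of death |
| General censoring rule (both documents) | Does not apply; the subject is not alive |
| No-assessment rule (SAP 5.4) | Censored at randomization |
| OS definition (SAP 5.4) | Event on the date of death |

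Under the SAP section 5.2 formula (event date minus start date plus 1), censoring at randomization gives a PFS time of 1 day. The subject leaves the risk set before any later event.

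**Coherence check.** If every death is a PFS event, PFS cannot exceed OS. Inputs: 125 subjects per group (SAP section 3). Assumptions: *d* deaths without an assessment in one arm, and no other event or censoring before week 12. With deaths counted, week-12 PFS is 1 − *d*/125, the same as OS. Under the literal rule it is 100%.

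| *d* | PFS, deaths counted (= OS) | PFS, literal rule | Excess of PFS over OS |
|---|---|---|---|
| 0 | 100% | 100% | 0 |
| 1 | 99.2% | 100% | 0.8 points |
| 2 | 98.4% | 100% | 1.6 points |
| 3 | 97.6% | 100% | 2.4 points |
| 5 | 96.0% | 100% | 4.0 points |

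**Effect on the hazard ratio.** The plan gives no PFS event count or rate, so there is no figure to reproduce. For illustration, assume 125 dosed subjects per arm, 10 other PFS events per arm, and two unassessed deaths, both in the ABP 798 arm. Approximate the hazard ratio by the ratio of event counts, with SE(log HR) = √(1/e₁ + 1/e₂).

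- Deaths counted: HR = 12/10 = 1.20; SE = √(1/12 + 1/10) = 0.43; 95% CI 0.52 to 2.78; 1-sided 95% upper limit 2.43.
- Deaths censored at randomization: HR = 10/10 = 1.00; SE = √(1/10 + 1/10) = 0.45; 95% CI 0.42 to 2.40; 1-sided 95% upper limit 2.09.

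A Cox fit to constructed data (deaths at days 30 and 45, other events spread over days 84 to 196) gives 1.21 (0.52 to 2.81) and 1.01 (0.42 to 2.43), so the approximation is adequate.

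Week-28 PFS in the ABP 798 arm is 1 − 12/125 = 90.4% with the deaths counted and 1 − 10/123 = 91.9% with them censored. The two deaths are 2/12 = 17% of that arm's events.

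**Varying the assumptions.**

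| Other events per arm | Unassessed deaths (ABP 798, rituximab) | HR, counted | HR, literal rule |
|---|---|---|---|
| 5 | 2, 0 | 7/5 = 1.40 | 1.00 |
| 10 | 2, 0 | 12/10 = 1.20 | 1.00 |
| 20 | 2, 0 | 22/20 = 1.10 | 1.00 |
| 10 | 1, 0 | 11/10 = 1.10 | 1.00 |
| 10 | 1, 1 | 11/11 = 1.00 | 1.00 |
| 10 | 0, 0 | 10/10 = 1.00 | 1.00 |

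The hazard ratio moves only when the unassessed deaths are unevenly split. The Kaplan-Meier curve of any arm that has such a death moves regardless of the split.

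**The case against.** The strongest reply is that context supplies the missing word. The no-assessment sentence follows directly on the rule for living, progression-free subjects and fills the gap that rule leaves: a living subject never assessed after baseline has no later evaluation date at which to be censored. A subject who has died already has an event. The protocol synopsis points the same way, since it has PFS and OS analyzed with all events up to the last subject's end-of-study visit, and the SAP says it is to be read with the protocol. This is very likely what the authors meant. But the synopsis statement does not mention unassessed subjects, and the SAP version in hand was written from protocol version 3.0 while the synopsis is from version 5.0. If anything, it adds a further statement with which the literal rule conflicts.

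Second, SAP section 10 requires derived datasets to be programmed twice and to match completely. That would expose two different readings, though the SAP would not settle which is right. It would not catch a dataset specification that copies the sentence as written, because both programmers would then agree on the wrong derivation.

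Third, the reach is small. Eligibility requires low tumor burden and ECOG 0 or 1, the PFS tables use dosed subjects, only the primary endpoint is inferential, and there may be no such deaths at all. The 1.2-to-1.0 shift also depends on placing both deaths in one arm. All of this stands. It limits the importance of the point but does not make the sentence correct.

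**Conclusion.** The point holds: the no-assessment rule is wrong as written. Followed literally, it censors deaths that the SAP's own definition and protocol section 12.6.7.4 count as PFS events, and no other passage resolves the conflict.

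It is a minor point. The consequence is confined to the descriptive PFS hazard ratios and Kaplan-Meier outputs. ORR is untouched, and OS and the fatal adverse event tables still show the deaths. On the assumed counts above, the hazard ratio changes by 0.4 at most (1.40 to 1.00, with five other events per arm and both deaths in one arm) and by nothing when there are no such deaths or they are balanced. With 10 other events per arm the shift lies well inside the confidence interval. No conclusion of the trial would change on these figures; they rest on assumed death and event counts, because the documents give none.

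**What to change.** In SAP2, replace the sentence with wording such as: *A subject who is alive and has no disease assessment after baseline is censored at randomization; a subject who dies without one has a PFS event on the date of death.* With that change, the open question of whether the clinical assessments at weeks 2 to 4 count no longer decides whether a death is an event.

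The cost is one sentence and the matching line in the derived-dataset specification. SAP section 1 already provides that "a final version of the SAP, known as SAP2, will be issued" before database lock, so the change fits the existing plan. No protocol amendment is needed, because the new wording agrees with protocol section 12.6.7.4. Making the change before lock also avoids settling the status of individual deaths once the data are known.
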